**Proprietary confidential information.**

© 2019 Boehringer Ingelheim International GmbH or one or more of its affiliated companies. All rights reserved.

This document may not - in full or in part - be passed on, reproduced, published or otherwise used without prior written permission.

Table 4.1.3: 2 Summary of dose adjustments based on trough dabigatran plasma concentration

Steady State Dose Range	Corresponding Action
Between 50 and < 250 ng/mL	Continue on same dose
Less than 50 ng/mL	Dose may be increased by 10-100%. Maximal allowed single dose in this study is 330 mg.
Greater than or equal to 250 ng/mL	Dose may be reduced by 25-50%

The reduction of a dose is not expected to result in concentrations < 75 ng/mL, but should be sufficient to avoid high concentration of  $\geq 250$  ng/mL. Blood sampling to measure trough dabigatran concentration (derived from dTT or alternative method) will be repeated at least 3 days (after at least 6 adjusted consecutive dabigatran etexilate doses have been taken), but no later than 6 days after dose adjustment, to confirm the new dose. After dose adjustment, the total dabigatran trough concentration should be between 50 and < 250 ng/mL.

If a patient cannot reach trough plasma concentrations between 50 and < 250 ng/mL after one dose adjustment, they must discontinue the study medication.

Due to the dabigatran etexilate limit of 22.2 mg/kg/day (based on excipient acceptable daily intake) as well as the maximal dabigatran etexilate single dose of 330 mg, up-titration will not be feasible in all instances. Likewise down-titration will not be possible in all cases due to unavailability of required dosages, see [Appendix 10.4.2](#). Affected patients have to be discontinued from dabigatran etexilate once the defined plasma trough concentration between 50 and < 250 ng/mL is not reached.

During the course of the study, the DMC can recommend further refinement of the target therapeutic trough steady state dabigatran concentrations based on data from ongoing paediatric studies or if emerging data from other dabigatran etexilate studies in other populations suggest that wider or narrower total dabigatran trough concentration range is associated with better benefit / risk ratio.

#### 4.1.4 Drug assignment and administration of doses for each patient

At Visit 2 patients who meet all eligibility criteria will be assigned to receive dabigatran etexilate (as capsules or pellets to be sprinkled on food or oral liquid formulation based on age and weight and ability to swallow capsules or pellets).

For patients who have been treated with VKA, Visit 2 should take place only if INR is  $\leq 2.3$  otherwise it should be postponed. The patient will start the study medication on the day of Visit 2 if INR is below 2.0 or on the next day if the INR is between 2.0 and 2.3.

Proprietary confidential information.

© 2019 Boehringer Ingelheim International GmbH or one or more of its affiliated companies. All rights reserved.

This document may not - in full or in part - be passed on, reproduced, published or otherwise used without prior written permission.

Patients who have been treated with parenteral anticoagulants should start the study medication 0-2 hours prior to the time that the next dose of the alternate therapy (e.g. LMWH) would be due, or at the time of discontinuation in case of continuous treatment (e.g. UFH).

The estimated dosages of dabigatran etexilate (as capsules, pellets to be sprinkled on food or oral liquid formulation) will be based on age and weight according to a nomogram provided in [Appendix 10.4.1](#). Patients who completed the treatment period of study 1160.106 receiving dabigatran etexilate may continue taking the same dose and formulation also in this trial.

Patients aged  $\geq 8$  years will be assigned to take capsules. In case a patient aged  $\geq 8$  years but below 12 years of age is unable to take capsules (per investigator judgment), they will be assigned to take pellets sprinkled on food. Patients  $< 8$  years of age are scheduled to receive pellets sprinkled on food. OLF may be used for patients who are  $< 12$  months of age. For patients  $< 12$  months of age OLF is preferred over pellets provided that OLF supplies are available to the site.

Dabigatran etexilate should be taken in the morning and in the evening, at approximately the same time every day. The capsules must not be crushed, not opened and can be taken with or without food. Dabigatran etexilate should be taken with a glass of water to facilitate delivery to the stomach. If gastrointestinal symptoms develop it is recommended to take dabigatran etexilate with a meal and/or a proton pump inhibitor according to the locally approved labelling recommendations. For paediatric patients receiving dabigatran and who suffer from dyspeptic symptoms, it should be taken into account that the local approval status as specified in the Prescribing Information or Product Information may vary between proton pump inhibitors and across countries. Therefore, the local standard of care in accordance with local labelling recommendations for proton pump inhibitors should be followed when treating gastrointestinal symptoms in paediatric patients treated with dabigatran. Alternative measures, such as taking dabigatran with a meal, should be considered if the local labelling recommendations and standard of care do not allow for the use of proton pump inhibitors in certain age groups and/or individual patients.

Pellets should be mixed with food (examples may include baby rice cereal, carrot mush, banana mush, strawberry jam, apple juice or apple sauce) and should be taken in its entirety (pellets and food) at every dose. The volume of the OLF must be taken in its entirety at every dose. The instructions for preparation of the OLF and pellets will be provided in the ISF. Younger patients must be assisted by the parent / legal guardian or an appropriate caregiver to ensure that the dabigatran etexilate dose is properly taken.

The interval between dabigatran etexilate doses should be as close to 12 hours as possible. If a dose of dabigatran etexilate is missed for any reason, the forgotten dose may still be taken up to six hours prior to the next scheduled dose otherwise the missed dose should be omitted and the next dose should be taken as scheduled. A double dose to make up for missed individual doses must never be taken. In addition, if a dose has only been taken partially, there should be no attempt to administer a second dose at that time-point, and the next dose should be taken as scheduled approximately 12 hours later.

**Proprietary confidential information.**

© 2019 Boehringer Ingelheim International GmbH or one or more of its affiliated companies. All rights reserved.

This document may not - in full or in part - be passed on, reproduced, published or otherwise used without prior written permission.

Patients will be treated with dabigatran etexilate until the clinical risk factor that necessitated further anticoagulant use has resolved, however for a maximum of 12 months. At the end of the study, all patients need to discontinue dabigatran etexilate, or switch to standard of care, if there is continued need for anticoagulant treatment (see [Appendix 10.3](#) for recommendations for transition to a non-study antithrombotic treatment with early study drug discontinuation or at the end of the trial).

In the event that a patient decides to discontinue dabigatran etexilate and has to be switched to non-study treatment according to the local practice, the Investigator should plan this transition taking into consideration the patient's risk profile and previous experience with anticoagulants. As patients have different risk profiles, optimal approaches might differ between patients and not all possible approaches can be fully outlined.

The transition plan will be up to the Investigator's judgment based on the patient's medical history and prior therapy experience (see [Appendix 10.3](#) for further guidance). Close monitoring of the patient's coagulation profile during the transition period must be implemented to optimize safety. In general, dabigatran etexilate therapy should not overlap with other anticoagulation therapy.

Investigators should recognise that the presence of dabigatran etexilate could elevate the INR. Once dabigatran etexilate has been stopped for >2 days, the INR will better reflect the effect of VKA therapy alone.

#### **4.1.5 Blinding and procedures for unblinding**

##### **4.1.5.1 Blinding**

This is an open-label, single arm prospective cohort study.

##### **4.1.5.2 Procedures for emergency unblinding**

Not applicable.

#### **4.1.6 Packaging, labelling, and re-supply**

For details of packaging and the description of the label, refer to the ISF.

#### **4.1.7 Storage conditions**

Dabigatran etexilate should be kept out of the reach of children and be stored protected from moisture and direct sunlight. Dabigatran etexilate capsules should be kept in their supplied container and the bottle lid must be kept closed. Dabigatran etexilate capsules must not be transferred to other types of containers.

The medication stick packs containing the dabigatran etexilate pellets should be kept sealed until just prior to intake.

The medication stick packs containing the dabigatran etexilate granules should be kept sealed until just prior to reconstitution, once reconstituted, the oral solution is stable for two hours at room temperature.

**Proprietary confidential information.**

© 2019 Boehringer Ingelheim International GmbH or one or more of its affiliated companies. All rights reserved.

This document may not - in full or in part - be passed on, reproduced, published or otherwise used without prior written permission.

Patients / parents / legal guardians should be instructed to keep medication containers tightly closed and not to remove capsules from original package material until immediately prior to the time of intake. Dabigatran etexilate may only be dispensed to trial patients (under supervision of their parent / legal guardian) fulfilling the inclusion and exclusion criteria by authorised study personnel as documented in the ISF. Receipt, usage, and return of the study medication must also be documented on the respective forms in the ISF. All unused medication including bottles and outer boxes (empty or filled) must be either returned to the Sponsor, or, following written authorisation from the Sponsor, may be destroyed at site if applicable. Receipt, usage and return must be documented on the respective forms. Reasons for any discrepancies must be thoroughly documented.

A temperature log must be maintained at the site to make certain that the drug supplies are stored at the correct temperature. For storage conditions refer to the locally approved medication label and the STORM document in the ISF.

Detailed instructions for the preparation and / or reconstitution of dabigatran etexilate (when applicable) and for dispensing and intake of dabigatran etexilate formulations (capsules, pellets and OLF) will be placed in the ISF.

#### **4.1.8 Drug accountability**

Drug supplies, which will be provided by the Sponsor, must be kept in a secure, limited access storage area under the storage conditions defined by the Sponsor.

The Investigator / pharmacist / investigational drug storage manager will receive the investigational drugs delivered by the Sponsor when the following requirements are fulfilled:

- approval of the study protocol by the IRB / ethics committee,
- availability of a signed and dated clinical trial contract between the Sponsor and the Head of Trial Centre,
- approval / notification of the regulatory authority, e.g. competent authority,
- availability of the curriculum vitae of the principal investigator,
- availability of a signed and dated clinical trial protocol or immediately imminent signing of the clinical trial protocol,
- if applicable, availability of the Form 1572.

The investigator / pharmacist / investigational drug storage manager must maintain records of the product's delivery to the trial site, the inventory at the site, the use by each patient, and the return to the Sponsor or alternative disposition of unused medication.

These records will include dates, quantities, batch / serial numbers, expiry ('use by') dates, and the unique code numbers assigned to the investigational product and trial patients. The investigator / pharmacist / investigational drug storage manager will maintain records that document adequately that the patients were provided the doses specified by the CTP and reconcile all investigational product received from the Sponsor. At the time of return to the Sponsor / appointed CRO, the investigator / pharmacist / investigational drug storage

**Proprietary confidential information.**

© 2019 Boehringer Ingelheim International GmbH or one or more of its affiliated companies. All rights reserved.

This document may not - in full or in part - be passed on, reproduced, published or otherwise used without prior written permission.

manager must verify that all unused or partially used drug supplies have been returned by the clinical trial patient and that no remaining supplies are in the investigator's possession.

## 4.2 CONCOMITANT THERAPY, RESTRICTIONS, AND RESCUE TREATMENT

Any additional drugs considered necessary for the patient's welfare may be given at the discretion of the investigator and with due consideration of the information provided in this protocol and the IB.

Details of concomitant medication administered to the patient during the course of the study should be recorded in the eCRF. This includes all concomitant therapies from time of patient screening until the patient completes follow up.

Certain concomitant therapies or surgery / intervention may require the temporary discontinuation of dabigatran etexilate. Study medication should be restarted as soon as safely possible.

At the Screening Visit, the site must document details of the anticoagulant therapy given for the treatment of the acute VTE.

### 4.2.1 Rescue medication, emergency procedures, and additional treatment(s)

The Investigator is responsible for ensuring that procedures and expertise are available to cope with medical emergencies during the study (also refer to [Section 5.2](#)).

Major bleeds for patients on dabigatran:

If a patient experiences a major bleed, dabigatran etexilate should be stopped and the source of bleeding investigated and treated. This will generally involve coagulation testing (e.g. activated partial thromboplastin time (aPTT), TT, dTT (where available), ecarin clotting time (ECT), platelet count), and possibly transfusion, diagnostic procedures and / or surgical haemostasis.

There is currently no specific reversal agent commercially available to counteract the antithrombotic activity of dabigatran in children, however such is in development ([P15-06362](#)). If a clinical study with specific reversal agent in paediatric patients is approved by the local health authority and ethic committees during the course of this study, instructions on how to use the specific reversal agent in appropriate cases or conditions and the requirements of participation in the respective clinical studies may be provided to the investigators. In such cases cross reporting of lab results might be applied in order to limit the blood volume required for analysis.

Since dabigatran is excreted predominantly by the renal route adequate diuresis must be maintained. Appropriate standard treatment, e.g. surgical haemostasis as indicated and volume replacement should be undertaken as appropriate. In addition, consideration may be given to the use of fresh frozen plasma ([P10-03790](#)). As protein binding is low, dabigatran is

**Proprietary confidential information.**

[figure not shown]
© 2019 Boehringer Ingelheim International GmbH or one or more of its affiliated companies. All rights reserved.

This document may not - in full or in part - be passed on, reproduced, published or otherwise used without prior written permission.

dialyzable, however there is limited clinical experience in this setting. The amount of drug cleared by dialysis is proportional to the blood flow rate.

There is some experimental evidence to support the role of agents such as activated prothrombin complex concentrates (APCC, e.g. FEIBA), recombinant Factor VIIa and three or four factor concentrates (Factors II, IX and X with or without Factor VII) in reversing the anticoagulant activity of dabigatran. The usefulness in clinical settings has not yet been systematically demonstrated. Consideration should also be given to administration of platelet concentrates in cases where thrombocytopenia is present or long-acting antiplatelet drugs have been used. All symptomatic treatment has to be given according to the physician's judgment.

A summary of how to manage bleedings on dabigatran etexilate is outlined in Figure 4.2.1: 1.

 for bleeding definitions see Section 5.2.1

 when appropriate

 recommendations based on limited clinical or non-clinical data only, limited or no experience in volunteers or patients

Figure 4.2.1: 1 Management of bleeding on dabigatran therapy ([P10-03790](#))

Proprietary confidential information.

© 2019 Boehringer Ingelheim International GmbH or one or more of its affiliated companies. All rights reserved.

This document may not - in full or in part - be passed on, reproduced, published or otherwise used without prior written permission.

Dabigatran etexilate must be stopped if a major bleeding event is observed. Initiation of any other alternative therapy for secondary VTE prevention after complete haemostasis has been achieved is at the Investigator discretion.

Clinically relevant non-major bleeds or minor bleeds:

If a patient experiences a clinically relevant non-major bleed or minor bleed, dabigatran etexilate may be continued, temporarily interrupted or permanently discontinued, at the discretion of the Investigator. It is not a requirement, however, that study drug be stopped in these cases.

Management of dabigatran etexilate prior to and after planned surgery:

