### 3.3.4 Removal of patients from therapy or assessments

#### 3.3.4.1 Removal of individual patients

An individual patient is to be withdrawn from the trial if:

- The patient / parent / legal guardian withdraws consent, without the need to justify the decision.

An individual patient is to be discontinued from trial treatment, but will remain part of the study and analysis population:

- If the patient is no longer able to take trial medication for other medical reasons (e.g. surgery, AEs, other diseases or concomitant therapies).
- If the patient is noncompliant with study drug administration despite all possible efforts.
- If, in the opinion of the Investigator, continuation on the study drug is not in the patient's best interest, if eligibility criteria are being violated, or if the patient fails to comply with the protocol (e.g. non-attendance at trial assessments).
- In the event that a recurrent thromboembolic event as assessed by appropriate imaging modalities is observed or if the patient experiences a drug-related significant or drug-related serious AE or if drug toxicity is observed.
- If the patient does not reach a total dabigatran plasma trough concentration within the pre-specified therapeutic range after one dose adjustment.
- If the patient becomes pregnant or a pregnancy is suspected during the trial the patient will be discontinued from the dabigatran treatment and will be put on an appropriate therapy per investigator judgment. The patient will be followed up until the end of the study and until the birth or otherwise termination of the pregnancy. For further information, including the process for follow up on the outcome of the pregnancy please see [Section 5.2.2.2](#).
- If a patient develops an active meningitis, encephalitis, or intracranial abscess.

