#### Clinically relevant non-major (CRNM) bleeding:

- Overt bleeding for which a blood product is administered and which is not directly attributable to the patient's underlying medical condition
- Bleeding that requires medical or surgical intervention to restore haemostasis, other than in an operating suite.

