#### Serious adverse event

A serious adverse event (SAE) is defined as any AE which results in death, is immediately life-threatening, results in persistent or significant disability / incapacity, requires or prolongs patient hospitalisation, is a congenital anomaly / birth defect, or is to be deemed serious for any other reason if it is an important medical event when based upon appropriate medical judgment which may jeopardise the patient and may require medical or surgical intervention to prevent one of the other outcomes listed in the above definitions.

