#### Causal relationship of adverse event

Medical judgment should be used to determine the relationship, considering all relevant factors, including pattern of reaction, temporal relationship, de-challenge or re-challenge, confounding factors such as concomitant medication, concomitant diseases and relevant history. Assessment of causal relationship should be recorded in the case report forms.

- Yes: There is a reasonable causal relationship between the investigational product administered and the AE.  
No: There is no reasonable causal relationship between the investigational product administered and the AE.

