### 7.3.3 Safety analyses

The safety analyses will be descriptive in nature and will be based on BI standards. Parameters to be evaluated for safety are described in [Section 5.2](#).

AEs will be coded using the MedDRA dictionary. All AEs will be classified according to the following trial periods: screening, treatment, safety follow-up. All AEs with an onset date / time after administration of trial medication up to 3 days after the last intake of study medication will be assigned to the treatment period for evaluation. In addition, AEs with onset date before start of the trial treatment but with worsening in intensity during the treatment will also be assigned to the on-treatment period. Other AEs will be assigned to the screening or post-treatment period, respectively. All AEs (including bleeding) in the treatment period will be tabulated in total and according to seriousness, severity and possible relationship to trial medication. AEs in the screening or follow-up period will be listed.

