Section to be changed		Flow Chart Section 3.3.4.1 Removal of individual patients
Description of change		The preferred way of follow-up of patients who have discontinued study medication prematurely (eEOT, Follow-up Visit 12 after 28 days, further follow-up according remaining visit schedule) was implemented consistently throughout the protocol.
Rationale for change		To clarify the preferred way of follow-up of patients who have discontinued study medication prematurely.

Section to be changed		Flow Chart, Footnotes 9 and 10 Section 3.1.1.3 Central laboratory Section 5.2.3 Assessment of safety laboratory parameters
Description of change		The exceptions from the generally central laboratory assessments were implemented consistently throughout the protocol.
Rationale for change		To align the wording related to exceptions from central laboratory assessments between relevant protocol sections.

Section to be changed		Section 3.3.4.1 Removal of individual patients
Description of change		A Patient is to be discontinued from study medication if he experiences a drug-related significant or serious AE. This was changed to “a drug-related significant or drug-related serious AE”.
Rationale for change		To clarify that the discontinuation from study medication is required in case of drug-related serious AEs, but not required in case of serious AEs that are not drug-related.

Proprietary confidential information.

© 2019 Boehringer Ingelheim International GmbH or one or more of its affiliated companies. All rights reserved.

This document may not - in full or in part - be passed on, reproduced, published or otherwise used without prior written permission.

Section to be changed		Section 4.1.3 Selection of doses in the trial
Description of change		It was added that the steady state of the currently assigned dabigatran etexilate formulation (i.e. at least 6 consecutive dabigatran etexilate doses have been taken) has to be achieved before a formulation switch could be considered. It was added that dabigatran etexilate up- or down-titration is not possible in some instances (limit of 22.2 mg/kg/day based on excipient acceptable daily intake, maximal single dose of 330 mg, unavailability of dosages) and affected patients have to be discontinued from dabigatran etexilate prematurely.

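### Section 4.2.1 tells sites that study drug need not be stopped after any CRNM or minor bleed, but Section 3.3.4.1 requires stopping when that bleed is a drug-related serious or significant AE

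*Protocol*

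**What the plan says.** Section 4.2.1 deals with bleeding by category. After a major bleed, dabigatran must be stopped. After a CRNM or minor bleed, "dabigatran etexilate may be continued, temporarily interrupted or permanently discontinued, at the discretion of the Investigator", followed by "It is not a requirement, however, that study drug be stopped in these cases". That paragraph names no exception for serious, significant or drug-related bleeds and does not point to the removal rules.

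Section 3.3.4.1 lists the circumstances in which a patient is to be taken off trial treatment while staying in the study and the analysis population. One of them applies "if the patient experiences a drug-related significant or drug-related serious AE or if drug toxicity is observed". The list makes no exception for bleeds.

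Section 11 (Amendment 07) explains the intent behind both sections. The rationale for the change to 3.3.4.1 says that "the discontinuation from study medication is required in case of drug-related serious AEs", but not for serious AEs that are unrelated to the drug. The same amendment removed the option to restart dabigatran after a major bleed, and the reason given was to bring 4.2.1 into line with 3.3.4.1.

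**The concern.** The two rules use different criteria. Section 4.2.1 goes by bleed category, and 3.3.4.1 goes by seriousness, significance and drug-relatedness. One event can satisfy both, and then one section allows treatment to continue while the other forbids it. A clinician managing a bleed will naturally turn to the bleeding section, and that section gives the permissive answer.

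At stake is whether a child who has had a drug-related serious bleed on an anticoagulant stays on it against the protocol's own stopping rule. The protocol states that no specific reversal agent is available for children. Sites could also handle identical events differently. That would change time on drug and, with it, the later AEs that are tabulated as on-treatment, because Section 7.3.3 says that AEs with onset "up to 3 days after the last intake of study medication will be assigned to the treatment period", whereas AEs in follow-up are only listed.

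**Working it through.** The plan gives no figure to reproduce here. The check is whether a single event can meet both rules.

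1. **Bleed category (Section 5.2.1).** A bleed is CRNM if a blood product is given and the bleed is not directly attributable to the underlying condition, or if it meets this criterion: "Bleeding that requires medical or surgical intervention to restore haemostasis, other than in an operating suite". Neither criterion refers to seriousness.
2. **Seriousness (Section 5.2.2.1).** An AE is serious if, among other criteria, it "requires or prolongs patient hospitalisation", or if it is an important medical event. Neither depends on bleed category, so a CRNM bleed that leads to admission is an SAE.
3. **Relatedness (Section 5.2.2.1).** The investigator answers yes or no. Yes means: "There is a reasonable causal relationship between the investigational product administered and the AE". For a bleed on an anticoagulant, that answer is plainly available.
4. **Bleeds count as AEs (Section 7.3.3).** Bleeding is included in the AE tabulations by seriousness and relationship, so the AE-based stopping rule covers it.

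Putting the rules side by side:

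| Event | Section 4.2.1 | Section 3.3.4.1 | Consistent? |
|---|---|---|---|
| Major bleed | Stop | Stop if drug-related and serious or significant | Yes |
| CRNM or minor bleed that is unrelated, or neither serious nor significant | Investigator's choice | Not triggered by this criterion | Yes |
| CRNM or minor bleed, drug-related and serious or significant | Investigator's choice; stopping not required | Stop | **No** |

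The conflict is confined to the last row. Stopping satisfies both sections there. Continuing, or interrupting and then resuming, satisfies only 4.2.1.

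**Upper bound on extra exposure for one affected patient**, from the nominal visit days in the Flow Chart, as days remaining to Visit 11 (day 365):

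- Bleed at Visit 6 (day 85): 365 − 85 = 280 days
- Bleed at Visit 8 (day 183): 365 − 183 = 182 days

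The protocol gives no expected rate of CRNM or minor bleeds, and no share of them that is drug-related and serious or significant. No count of affected patients can be calculated.

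**The case against.** The best counter-argument is that the rules are cumulative. On that reading, 4.2.1 says only that a non-major bleed does not by itself force a stop, in contrast to a major bleed, and 3.3.4.1 still applies as the dedicated removal section. A careful reader could reconcile the text this way, and permanent discontinuation is among the options 4.2.1 lists. But 4.2.1 is not silent on the matter. It grants the choice to the investigator and states that stopping is not required, with no limit. Nor did the sponsor leave major bleeds to a cumulative reading: Amendment 07 rewrote that text to match 3.3.4.1. Leaving the CRNM and minor paragraph discretionary could have been deliberate, but for a drug-related serious bleed it would then conflict with the rationale given for 3.3.4.1.

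Existing safeguards also count. Clinically relevant bleeds and SAEs call for an unscheduled visit, preferably within 24 hours; SAEs are reported to the sponsor within 24 hours; and the DMC reviews safety on an ongoing basis. These make a missed stop likely to be noticed, so the full 280 or 182 days is improbable. They detect a wrong decision and do not correct the instruction that led to it.

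Three further limits stand:

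- The protocol text does not define a significant AE, so that edge of the overlap is unclear. The serious-AE overlap does not depend on it.
- For minor bleeds the overlap is narrower than for CRNM bleeds, since by definition they needed no intervention to restore haemostasis.
- Figure 4.2.1: 1 is not visible in the document reviewed and might carry a qualifier. The finding concerns the written text only.

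**Conclusion.** The concern holds. For CRNM or minor bleeds that are also drug-related serious or significant AEs, Section 4.2.1 permits what Section 3.3.4.1 forbids. The number of patients affected is probably small, but the documents do not allow an estimate. The day counts are ceilings: they assume the patient would otherwise have stayed on drug to day 365, that the risk factor does not resolve earlier, and that nobody corrects the decision.

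The consequence is for patient safety and consistency between sites. AEs would still be classified correctly against actual last intake; what changes is the exposure itself. The primary Kaplan-Meier estimates are not threatened, because the first bleed is counted before any decision about stopping and patients who stop drug remain in the analysis population. The correction should be made, but it does not call the design into question.

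**What to change.** In the CRNM and minor bleed paragraph of Section 4.2.1, add an exception: the investigator's discretion does not apply if the bleed is a drug-related serious or drug-related significant AE, in which case dabigatran etexilate must be discontinued in line with Section 3.3.4.1. Check that Figure 4.2.1: 1 gives the same instruction. This extends to non-major bleeds the alignment that Amendment 07 made for major bleeds.

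The cost is one clause in the next amendment and a notice to sites. No visits, patients or analyses are added.
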